8.9.2.4 Tumor Response Rate

The ORR will be computed for the two treatment groups as proportion of CR+PR over the total number of patients in the specified population. The 95% CIs for the ORR for each of the treatment groups will be computed according to Wilson (1927).

ORR, as determined by the investigator will be compared between treatment groups using the continuity adjusted Newcombe-Wilson test, and the corresponding 95% CI for the difference in ORRs between the two treatment groups will be calculated. This analysis will be performed under RECIST 1.1, mRECIST, and EASL for each time point and the best overall response.

DCR (ie, CR+PR+SD) will be summarized and compared between the treatment groups in the same way as the ORR.

Details on target lesions and non-target lesions will be presented in listings only.

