## 9.2.17 Efficacy Imaging – CT/MRI

Baseline efficacy imaging scans will be obtained during screening and efficacy assessment scans will be taken every 8 weeks post randomization until progression is confirmed (see Section 9.2.20). Most patients will be evaluated by CT images. MRI images are also permitted. The imaging modality used at baseline must continue to be used for all efficacy images throughout the study. Triple phase CT will be used in accordance with site standards at baseline for dosimetry determination. SPECT imaging may be performed according to standard of care practices for clinical management but is not a study requirement.

Spiral CT abdomen/pelvis – must be performed with cuts of 10 mm or less in slice thickness contiguously in the axial plane. From these images, hepatic and extra-hepatic lesions will be read.

Spiral CT Chest – must be performed with cuts of 10 mm or less in slice thickness contiguously in the axial plane. From these images, extra-hepatic lesions will be read.

To enable analysis of secondary study endpoints using radiological assessment, investigators will identify, read and use bidimensional measurements of target lesions for size and will record evidence of enhancement and increase in dimension of a pre-existing thrombus for all image timepoints. These data will be captured on the eCRF. Comparison between baseline and subsequent images of quantitative and qualitative findings will determine response according to RECIST v 1.1, mRECIST and EASL which are assessed separately in secondary endpoint analyses.

Bone Scintigraphy – Bone scintigraphy to assess spread of metastatic disease will be performed according to institutional standards. For patients with AFP > 400 ng/mL at screening, results of bone scintigraphy will be recorded at the screening visit and subsequent study visits according to the site standard practice ( week 16 study visit and 6 months thereafter (i.e. months 10, 16, 22, etc.) ). Bone scintigraphy is suggested whenever there is an unjustified increase in AFP or the patient experiences bone pain or symptomatic deterioration and repeated at a frequency according to site standard practice.

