5 CHANGES IN THE CONDUCT OF THE STUDY OR PLANNED ANALYSES

This SAP is based on protocol version 3.0 dated 08 August 2014. Due to challenges with patient recruitment the study was terminated prematurely; therefore, only a final analysis will be performed without any interim analyses..

Protocol section 10.2.3.2 states that time to progression (TTP) will be calculated as the interval between the randomization date and the date of first disease progression as defined by the respective criteria noted below, death for any cause or of last contact for patients alive. However, death will not be considered in the calculation of TTP. Section 6.4.2.1 of this SAP explains how TTP will be analyzed.

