6.4.2.4 Tumor Response Rate (ORR and DCR)

Tumor Response is based on the radiological tumor assessment performed at specified time points. The post baseline assessments are compared to the baseline assessment and the overall response based on investigator assessment is recorded at each efficacy visit. The tumor response is categorized as Complete Response (CR), Partial Response (PR), Stable Disease (SD) or Progressive Disease (PD). There are three sets of criteria that will be assessed, RECIST 1.1, mRECIST, and EASL.

The best overall response is the best response recorded during the study. It will be determined from the overall responses derived at each efficacy visit using the rules according to the tables in Appendix 3.

The ORR is defined as the proportion of patients achieving a best overall response of confirmed CR, or PR. The disease control rate (DCR) is defined as the proportion of patients achieving a best overall response of confirmed CR, PR, or SD.

Patients who do not have any post baseline tumor assessments for any reason are considered non-responders and are included in the denominator when calculating the response rate.

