8 STATISTICAL ANALYSIS

8.1 Disposition of Patients

The number of patients enrolled by region (North America, Europe and Asia), country and site will be presented.

The number of patients screened, the number of patients randomized, and the number of patients treated with the treatment to which they were randomized (ie, sorafenib or TheraSphere) will be summarized.

The number of patients who completed or were ongoing at the end of the study will be summarised. Note: patients who died will be considered as having completed the study.

The number of patients who discontinued from the study will be summarized overall and separately for those who were treated with TheraSphere or sorafenib. The reasons for discontinuation will be summarized for patients by treatment group.

This information will be summarized also by the stratification factor AFP \leq 400 ng/mL or >400 ng/mL).

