8.9 Analysis of Efficacy Parameters

Efficacy endpoints will be analysed using the Treated Population.

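### By-visit ORR and DCR are divided by the whole Treated Population, so after early closure any patient whose scan was not yet due dilutes the rate and the between-arm difference.

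*SAP*

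**What the plan says.** SAP 8.9.2.4 fixes the denominator: "The ORR will be computed for the two treatment groups as proportion of CR+PR over the total number of patients in the specified population". SAP 8.9 identifies that population: "Efficacy endpoints will be analysed using the Treated Population". SAP 8.9.2.4 then sets the scope, after describing the between-arm test and confidence interval: "This analysis will be performed under RECIST 1.1, mRECIST, and EASL for each time point and the best overall response". Disease control follows the same rule: "DCR (ie, CR+PR+SD) will be summarized and compared between the treatment groups in the same way as the ORR".

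The only rule for missing assessments is in SAP 6.4.2.4: "Patients who do not have any post baseline tumor assessments for any reason are considered non-responders and are included in the denominator". It covers patients with no post-baseline scan at all. It does not address a patient with some scans whose next one was never due.

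On closure, SAP section 5 says: "Due to challenges with patient recruitment the study was terminated prematurely". SAP 8.1 provides a matching disposition line: "The number of patients who completed or were ongoing at the end of the study will be summarised". Under Protocol 9.2.17, "efficacy assessment scans will be taken every 8 weeks post randomization until progression is confirmed".

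Neither document limits the by-visit denominator to patients whose visit could have taken place before closure.

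**The concern.** A full denominator is the usual convention for best overall response. At a given visit, counting patients who had already died or progressed as non-responders is also reasonable. The difficulty is confined to patients whose visit date fell after the study closed. Someone in partial response at Week 16, with Week 24 due after closure, adds one to the Week 24 denominator and nothing to the numerator. That outcome is set by the randomisation date, not by treatment.

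The plan as designed largely avoided this. Protocol 10.1 foresaw a further year of follow-up after accrual, and Week 48 falls at 336/30.4375 = 11.0 months, so scans through Week 48 would have been due for every patient. Early termination removed that assurance. The SAP adapted other analyses to the termination: interim analyses (7.4.1), the site covariate (7.2) and subgroups (7.7) were dropped. The by-visit denominator was not adapted. Protocol 10.2.3.2 also divides by all patients, but it does not ask for rates at each time point; the SAP added those.

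At stake are the by-visit ORR and DCR tables under three response criteria and their between-arm comparisons. They would understate both rates and differences, increasingly at later visits, and the reader could not see it from the table.

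**Working it through.** The plan states no figure to reproduce. The check is what the stated rule estimates.

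**Inputs from the documents.** Fixed denominator at each time point (SAP 8.9.2.4); scans every 8 weeks (Protocol 9.2.17); Weeks 8, 16 and 24 at Days 56, 112 and 168 (SAP Table 4); visit tolerance ±7 days (Protocol 9.1); 1:1 randomisation (SAP 4.2). The number randomised, the number not yet due, the accrual period and the time from last randomisation to closure are not given, so they are assumptions below.

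**Step 1: effect of the rule.** Let p be the true by-visit rate, with earlier death or progression counted as failure, and c the fraction not yet due. If response does not depend on entry date:

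- expected rate under the SAP rule = p(1−c) + 0·c = p(1−c)
- expected difference, with the same c in both arms = (p1−p2)(1−c)

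**Step 2: possible values of c.** With uniform accrual over A months and F months of follow-up after the last randomisation, a visit at t months gives c = max(0, (t−F)/A). For Week 24, t = 168/30.4375 = 5.52. The last three columns show what a true DCR difference of 20 points (60% v 40%) becomes, 20 × (1−c).

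| A (months) | c, F = 0 | c, F = 3 | c, F ≥ 5.52 | Difference, F = 0 | Difference, F = 3 | Difference, F ≥ 5.52 |
|---|---|---|---|---|---|---|
| 12 | 46% | 21% | 0 | 10.8 | 15.8 | 20 |
| 24 | 23% | 10% | 0 | 15.4 | 17.9 | 20 |
| 36 | 15% | 7% | 0 | 16.9 | 18.6 | 20 |

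Adding the 7-day tolerance (t = 175/30.4375 = 5.75) moves the F = 0 values to 48%, 24% and 16%, and c reaches 0 at F = 5.75. With F = 0, earlier visits lose less: for A = 24, c is 1.84/24 = 8% at Week 8 and 3.68/24 = 15% at Week 16.

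**Step 3: estimate and precision.** Assume 40 per arm, c = 30% and a true ORR of 40% v 10%. That leaves 28 due per arm and about 11 v 3 responders. Intervals are Newcombe with continuity-corrected Wilson limits.

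- SAP rule: 11/40 − 3/40 = 20.0 points (95% CI 1.3 to 37.5)
- Patients due: 11/28 − 3/28 = 28.6 points (95% CI 3.2 to 50.1)

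The true difference is 30 points. The restricted denominator comes closer, at the price of an interval 46.9 points wide instead of 36.2.

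**Step 4: can the rule create a difference?** With equal true DCR of 50% and c = 20% v 40%, the table would show 40% v 30%. But entry date is fixed before randomisation. With 40 per arm and c = 30% overall, the standard error of the difference in c is √(2 × 0.3 × 0.7/40) = 10 points, so that imbalance is about a two-standard-error chance event. It is part of the sampling variation that the full-denominator test and interval already carry.

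**The case against.** The strongest reply is that this affects supplementary tables by an unknown and possibly zero amount. SAP 6.4.2.4 defines ORR and DCR through best overall response, where the full denominator is accepted. Disease control over time is also covered by TTP, which censors patients without progression instead of counting them as failures. The SAP never says in words that a visit not yet due is a failure; this follows only from the fixed denominator. These points stand, and they limit the weight of the concern. They do not remove it, because the rule is explicit and a between-arm comparison is attached to each time point.

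Three stronger readings are tempting, and the documents do not support them.

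- A reader might infer from SAP 8.1 that patients were in fact ongoing at closure. It only provides a category, whose count may be zero. Nor does ongoing mean that a scan was pending: patients are followed to death, but efficacy scans stop at confirmed progression.
- A reader might infer that the rule produces false differences between arms. As Step 4 shows, if the arms do not differ in response, the count observed over all patients has the same distribution in both. The systematic effect is attenuation towards no difference.
- A reader might take a halved difference as the expected size. That needs 12 months of accrual with follow-up ending on the day accrual ended. Termination for poor recruitment does not show that follow-up stopped then.

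**Conclusion.** The concern holds as a bias towards zero in by-visit ORR and DCR and in their between-arm differences, by a factor of about (1−c). At Week 24, c lies anywhere from 0 (follow-up of at least 24 weeks plus the tolerance after the last randomisation) to about 15% to 46% (uniform accrual over 36 to 12 months, no further follow-up). Later visits are more exposed. The size rests on assumed accrual and follow-up, and on response not depending on entry date.

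Type I error is not inflated, because entry time is independent of randomised arm. The rule does not touch best overall response, OS or TTP. The change is worth making because it is cheap and the dilution would otherwise be invisible, but it does not threaten the trial's main conclusions.

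**What to change.** In SAP 8.9.2.4:

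- Keep all Treated patients as the denominator for best overall response.
- For each time point, use the Treated patients whose scheduled visit day plus the 7-day tolerance (Days 63, 119 and 175 for Weeks 8, 16 and 24) fell on or before the study-closure or data cut-off date. Apply this by randomisation date alone. A patient not yet due is left out even if already progressed; otherwise failures would be kept and responders dropped.
- Within that group, count earlier death, progression, withdrawal or a missed scan as non-response.
- Show the number not yet due per arm at each time point.

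Requiring the whole Table 4 window to have closed would be too strict. The Week 16 window runs to Day 140, so a valid Day 112 scan would be lost if closure fell on Day 130; the rule above keeps it, since 119 ≤ 130.

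The cost is a short addition to the text, a stated cut-off date (the SAP defines none) and one table column, with no new data. By-visit denominators become smaller and confidence intervals wider at later visits. A few scans taken just before closure drop out of the by-visit tables but still count towards best overall response. If nobody was awaiting a visit, the results do not change and the new column shows it.

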8.9.2.5 Analysis of Quality of Life (FACT-Hep)

The total, domain, and individual question scores of the FACT-hep QoL instrument and their differences from baseline will be summarized at each time point by treatment group. The two treatment groups will be compared by applying a mixed linear model repeated measures analysis using a REML estimation with the treatment, visit and the interaction between treatment and visit as factors, and the baseline score as a covariate. An unstructured covariance approach will be applied. If the fit of the unstructured covariance structure fails to converge, the following covariance structures will be tried in order until convergence is reached: Toeplitz with heterogeneity, autogressive with heterogeneity, Toeplitz, and autoregressive. Means and least squares mean difference between treatment groups, along with a two-sided 95% CI and p-value for the difference between treatments will also be provided.

A deterioration in QoL is defined as a ≥7-point decline in the total FACT-hep score or death whichever occurs first.

TTDQoL quartiles will be presented and 95% CIs will be calculated on the quartiles for each treatment group. A log-rank (two-sided) test will be used to compare TTDQoL between the two treatment groups at a 0.05 significance level. The HR and corresponding 95% CI will be computed. Plots of the Kaplan-Meier curves will be provided for each treatment group.

8.9.3 Additional Analyses

A shift table comparing the baseline Child Pugh score to the Child Pugh score at each time-point will be summarized. This will be used to ascertain the number of patients with a Child Pugh score that changes after baseline and any difference between the treatment groups.

DpR will be summarized with descriptive statistics (n, mean, SD, median, min, and max) by treatment group.

ETS will be summarized with descriptive statistics (n, mean, SD, median, min, and max) by treatment group. The number of patients achieving an ETS of <10%, 10-20%, and >20% will also be summarized by treatment group.

The percentage and absolute change from baseline in the sum of the longest diameters of target lesions will be summarized separately at Week 8, 16, and 24 analysis visits (as defined in Table 4). A waterfall plot of the percentage change in the sum of longest diameters at the time of the best overall response will be presented.

The tumor marker for HCC (AFP) will be summarized with descriptive statistics (n, mean, SD, median, min, and max) for each time-point and change from baseline by treatment group. The number of patients achieving an AFP response, defined as a ≥50% decrease in AFP levels for patients with a baseline AFP level of ≥200 ng/mL, will also be summarized for each post-treatment time-point by treatment group.

8.10 Analysis of Safety

All safety analyses will be performed on the Safety Population.

8.10.1 Extent of Exposure to Study Treatment

8.10.1.1 Extent of Exposure to TheraSphere

The number of lobar treatments of TheraSphere received will be presented prior to progression, following progression and across the study.

A summary of dose delivered to a particular lobe prior to progression and following progression will be presented. In addition, whether the dose was delivered as planned, whether any prophylactic gastric inhibitor treatment was prescribed, whether there were any complications or device deficiencies will be summarized.

A summary of the dose delivered to the lungs will be summarized prior to progression, following progression and over all treatments.

8.10.1.2 Extent of Exposure to Sorafenib

The extent of patient exposure to sorafenib will be summarized using descriptive statistics (n, mean, sd, median, minimum, maximum) for the following parameters:

- Cumulative dose (mg)
- Dose intensity (mg/month)
- Relative dose intensity (%)
- Duration of treatment (months)

The reason of dose delays and changes will be summarized.

8.10.1.3 Extent of Study Exposure and Follow-up

The time to first TheraSphere treatment, time to first dose of sorafenib, duration of survival follow-up and duration of follow-up from last study treatment will be summarized by treatment using descriptive statistics (n, mean, sd., median, minimum, maximum). The time between TheraSphere administrations (first to second and second to third) will be summarized by treatment using descriptive statistics.

In addition, an alternative method for determining median duration of follow-up will be performed using the reverse Kaplan-Meier method, in which the censored values for the OS analysis will be reversed (ie, patients censored for the OS analysis will not be censored for the reverse Kaplan-Meier method, and patients not censored for the OS analysis will be censored for the reverse Kaplan-Meier method).

8.10.2 Adverse Events

The investigator's verbatim term of each adverse event will be mapped to system organ class (SOC) and preferred term (PT) using the MedDRA dictionary version 14.0.

An overall summary of adverse events will be presented including number and percentage of patients with any TEAEs, sorafenib related TEAE, adverse device effects

(ADEs), angiographic procedure-related TEAEs, TEAEs CTCAE grade ≥ 3, serious adverse events (SAEs), serious adverse device events (SADEs), TEAEs with outcome of death and TEAEs leading to discontinuation of sorafenib.

TEAEs will be summarized by SOC and PT; a patient will only be counted once per system organ class and once per PT within a treatment. Patient counts and percentages and event counts will be presented for each treatment group:

- Overall summary of AEs
- All TEAEs.
- All TEAEs of CTCAE grade ≥3.
- All TEAEs related to sorafenib.
- All TEAEs related to device (ADE).
- All CTCAE grade ≥3 TEAEs related to device.
- All TEAEs related to angiographic procedure.
- All TEAEs with outcome of death.
- All treatment emergent serious adverse events (SAEs).
- All treatment emergent serious adverse device events (SADEs)
- All TEAEs leading to sorafenib discontinuation.

For the summary of AEs by CTCAE grade, if a patient has multiple events occurring in the same SOC or same PT, then the event with the highest CTCAE grade will be counted. For AEs by relationship to study device, if a patient has multiple events occurring in the same SOC or same PT, the event with the highest association to study device will be summarized (unknown relationship to study device will be considered related to study device).

All TEAEs and TEAEs grade ≥3 will be summarized by preferred term with descending frequency. In addition TEAEs will be presented by CTCAE grade (1-2, 3-4 and 5).

No statistical inference between the treatments will be performed on AEs.

Listings will be presented by patient for all AEs as well as for SAEs including SADEs, AEs with outcome of death, and AEs leading to discontinuation of sorafenib.

8.10.3 Clinical Laboratory Evaluations

Laboratory test values at each assessment and for change from baseline to each assessment will be displayed using summary statistics (n, mean, median, and standard deviation).

In addition, shift tables will be presented to display the shift in the normal range categories (L, normal [N], H) from baseline to the final evaluation. Baseline is defined as the latest non-missing value prior to randomization.

Shift table of laboratory assessments with CTCAE grade ≥3 that also worsened from baseline will be presented by visit for each laboratory parameter.

Shift table of baseline to each assessment by CTCAE grade will be summarized. Laboratory tests with CTCAE grades in two directions (increasing and decreasing) will be presented separately for each direction.

All clinical laboratory data will be presented in listings. Within each listing, laboratory values outside the normal ranges will be flagged as either high (H) or low (L).

